Prior studies^{2,3,9,20} demonstrated that most patients obtain significant relief from TPI, but did not identify differences between injection of CS or other substances. However, none of these studies identified LTRs in their injection techniques.

As can be learned from a review of the published literature on muscular trigger points, the cause of this condition is unknown, and no single treatment approach has been established as a clearly accepted gold standard treatment. There is evidence, however, that there is an inflammatory component associated with trigger points and that obtaining a local twitch response is associated with a decrease in local inflammation at the site of a trigger point. The combination of injecting an anti-inflammatory medication and obtaining a local twitch response has never been studied. The purpose of this study is to examine the comparative effectiveness of injectable substances on patient outcome after a TPI with LTR identified, namely a CS (dexamethasone), a NSAID (ketorolac), or only a local anesthetic (lidocaine).

Purpose and Objectives

Hypothesis

The main hypothesis of this study is that anti-inflammatory medications (ketorolac or dexamethasone) will provide longer-lasting and greater pain relief than just lidocaine in trigger point injections where a local twitch response is evoked at the time of the injection.

Purpose/Specific Aims

The primary objective of this study is to compare the efficacy of three substances used in TPIs with a LTR identified at the time of the injection: a CS (dexamethasone), a NSAID (ketorolac), or only a local anesthetic (lidocaine).

Study Population

Age of Participants: 18-100

Sample Size:

At Utah: 60
All Centers: 60

Inclusion Criteria:

1. Men or women age 18 or over
2. At least one active trigger point, as defined by Simons and Travell

Exclusion Criteria:

1. Allergy or contraindication to any NSAID, CS, or local anesthetic
2. Receiving anticoagulant medication
3. History of bleeding disorder
4. Pregnant or breast feeding women
5. Gastrointestinal ulceration
6. Pre-existing renal disease
7. Pre-existing congestive heart failure
8. Diabetes mellitus
9. Prior myocardial infarction or stroke
10. Fibromyalgia

Design

Observational Research

Double Blind

Randomized

Study Procedures

Recruitment/Participant Identification Process:

Subject recruitment

Subjects will be recruited from the University of Utah Orthopaedic Center, Farmington Health Center, and South Jordan Health Center during an existing appointment. Participation in this study will not require any additional study-specific visits. Subjects requiring a TPI for treatment will be approached by a study team member who will provide a basic description of the study and review inclusion and exclusion criteria with the patient. If the patient is interested in participating, a member of the study team will obtain written informed consent. University of Utah physical therapists and physicians will be notified about this study and asked to help recruit appropriate subjects.

Informed Consent:

Description of location(s) where consent will be obtained:

University of Utah Orthopaedic Center, Farmington Health Center, and South Jordan Health Center

Description of the consent process(es), including the timing of consent:

Informed written consent will be obtained from all participants. The researcher will provide an explanation of the consent form and study details to these individuals. One of the investigators will always be available to speak with prospective participants that have questions. The potential participants can take as much time as they like until they choose to consent and do not have to consent on the same day the study is presented.

Procedures:

Consent process

Consent: Written informed consent will be obtained from all participants. The researcher will provide an explanation of the consent form and study details to each participant. One of the investigators will always be available to speak with prospective participants that have questions. Institutional Review Board approval will be granted through the University of Utah.

Study procedures

TPIs are a standard procedure performed by physicians. Regardless of participation in the research study, the procedure will be performed in the same manner. Participants will undergo TPIs by the following method. A 3mL syringe with any of the three medications listed below would be drawn by an assigned, unbiased, and unblinded health care professional (e.g. medical

assistant, nurse, etc.), leaving its contents unknown to the physician doing the injection. A 25g, 1.5" needle will be used for all injections. The needle will be inserted into the trigger point with the goal of eliciting a LTR. When a LTR is obtained, 0.1mL will be injected into that location within the muscle. This will be repeated until LTRs disappear, or 1.0mL has been injected, whichever comes first. This can be performed in a similar manner for all affected muscles, up to a maximum of 2mL.

Blinding: Both the physician performing the injection and the participant will be blinded to the medication injected. Only the assigned health care professional will be unblinded. Each substance is clear and cannot be distinguished from the other. The blinding procedure has been fully discussed and approved by the medical staff at all sites (UUOC, FHC, SJHC).

Study Drug Ordering: A study team member (with IDS assistance), will create a blinded study drug order in the medical record (Epic). This blinded study drug order will have a title similar to "study blinded ketorolac/dexamethasone/lidocaine injection, 2mL." When a participant enrolls, the blinded PI will place an order for the study drug. The assigned health care professional will access the participant's medical record to ensure the PI has placed and signed an order for study drug.

Randomization: A randomization schema will be created in Excel (with IDS assistance) by an unblinded study team member that will ensure even accrual numbers across the three different cohorts. Neither the blinded physician, nor the participant will have access to this document. A health care professional at each of the three participating sites will be unblinded and assigned to have access to this shared drive for purposes of randomizing newly enrolled participants and unblinding a participant in the event of an adverse reaction. This randomization document will be kept and maintained on uBOX (a secure shared drive). Once the assigned health care professional has confirmed that an order has been placed and signed by the blinded PI for study drug, they will access the randomization schema to obtain a randomization number. This randomization number will be either a 1, 2, or 3 and each number will correlate to a different study drug combination. The health care professional will draw up the randomly assigned study drug outside of the participant's room and hand-off the syringe to the PI for injection.

Medical Record Documentation: After the medication has been administered, the blinded PI or the physician who completed the injection will document the process in the medical record, specifying how much of the 2mL study drug was used for the injection.

Medication Inventory: Each of the three participating sites will have the same medications for use and they will be stored in locked cabinets and labeled for investigational use only. IDS will provide each site with a drug inventory log to document study drug usage. This drug inventory log will be monitored by the Data and Safety Monitoring Board at intervals specified in this application.

Unfortunately, the use of the local pharmacy (e.g. UUOC pharmacy or FHC pharmacy) will not be a feasible option. This will take at least 30 minutes extra to obtain the medication, for

which will be too time-intensive for most patients to tolerate. Additionally, this will interrupt regular clinic flow to a large degree.

All three medications used in this study have been shown to be safe, and are already used in a standard fashion for intramuscular injections; therefore, these medications will not pose undue risk to the participant. Furthermore, as lidocaine will be included in all injections, the participant will unlikely be able to differentiate which medication they received based off the presence or absence of short-term numbness.

The PI has successfully administered these drugs in the below mentioned dosages and combinations. From past experience, the PI does not express any safety concerns regarding the administration of these drug combinations.

Subsequent injections

Participants will be allowed to have subsequent injections, which is standard practice³⁹⁻⁴³. They may receive up to four injections, spaced at least 1 week apart. The assigned health care professional will access the randomization schema at each subsequent visit to identify which substance was injected at their previous visit and use that same substance for all subsequent injections. The primary time point will be maintained, and questionnaires will be administered.

Medications:

1. 1mL of 1% lidocaine + 1mL of 4mg/mL dexamethasone
2. 1mL of 1% lidocaine + 1mL of 30mg/mL ketorolac
3. 2mL of 1% lidocaine

Outcomes:

1. Pre- and post-injection numeric rating scale (NRS) from 0-10 with regards to the trigger point(s).
2. Survey questions

Primary outcome measure

1. Responder (>50% NRS relief)

Secondary outcome measures

1. NRS improvement
2. Brief pain inventory (BPI) improvement

Time points:

Participants will fill out a pre-injection survey that contains demographic information and pain- and function-related questions. Participants will also complete a survey at the following time points:

1. Immediately post-injection
2. 1 week post-injection
3. 2 weeks post-injection
4. 4 weeks post-injection
5. 3 months post-injection

Procedures performed for research purposes only:

TPIs are a standard procedure performed by physicians. Regardless of participation in the research study, the procedure will be performed in the same manner.

The research component of this study is to compare the efficacy of three substances used in TPIs with a LTR identified at the time of the injection: a CS (dexamethasone), a NSAID (ketorolac), or only a local anesthetic (lidocaine).

Statistical Methods, Data Analysis and Interpretation

Statistical plan:

Chi-square analysis will be used to identify differences in responders between groups. Repeated-measures ANOVA testing will be used to identify changes in pain scores.

Power Analysis:

Similar to the study by Gerber et al.⁴¹, if 5% of patients spontaneously improve their MTrP status without intervention and aiming for detection of 10% responders, a sample size of 90 subjects would be required. However, in their study, they found that this was substantially overpowered due to a much higher percentage of responders. We have identified a sample size of 60 subjects (20 per group) as being sufficient, based on the prior work being overpowered. As they had a much larger response rate in their actual cohort, we feel that a conservative estimate of 15% responders would be appropriate (as opposed to 10%), which yields a sample size around 60 total subjects.

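### The NRS analysis names neither its occasions nor its tested term, so a score taken under lidocaine can enter the efficacy comparison

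*Protocol*

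**What the plan says.** The Hypothesis section of the protocol expects that ketorolac or dexamethasone "will provide longer-lasting and greater pain relief than just lidocaine". Under Time points, five post-injection surveys follow the pre-injection one. The first is "Immediately post-injection"; the others are at 1, 2 and 4 weeks and 3 months. Nothing gives the first a different status.

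NRS improvement and BPI improvement are secondary outcomes. For the scores, the Statistical plan offers one sentence: "Repeated-measures ANOVA testing will be used to identify changes in pain scores". The SAP repeats it. Neither document lists the occasions, says how the pre-injection score is used, or names the term to be tested (arm, time or arm-by-time).

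The Medication Inventory section argues that blinding is protected "as lidocaine will be included in all injections", and so expects short-term numbness in all arms. The Medications list gives "1mL of 1% lidocaine + 1mL of 4mg/mL dexamethasone", "1mL of 1% lidocaine + 1mL of 30mg/mL ketorolac" and, for control, "2mL of 1% lidocaine".

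The primary outcome, more than 50% NRS relief, has no time attached. A primary time point is mentioned under Subsequent injections but never identified.

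**The concern.** The hypothesis is about relief that is greater and lasts longer than lidocaine gives. A score taken minutes after injection mainly reflects local anaesthetic and needling. If it is an ordinary occasion in the ANOVA, the harm depends on the term tested:

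- **Arm effect averaged over surveys:** a real later difference is averaged with an occasion at which little or no drug difference is expected.
- **Arm-by-time:** an arm difference present only at the immediate survey can produce significance, which could be reported as a lasting difference between substances.

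The responder outcome is open to the same gap, because nothing stops the immediate survey from being the one at which response is judged.

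**Working it through.** **Inputs from the documents.** 20 patients per arm and three arms (Power Analysis); one pre-injection and five post-injection scores (Time points); lidocaine content (Medications). The sample-size figure of 60 rests on responder proportions and gives no planning value for the NRS, so there is no stated figure to reproduce here.

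**Assumptions, not in the documents.** Alpha 0.05; both anti-inflammatory arms better than control by the same d = 1.5 points at the four later surveys, with no immediate difference. Base case: SD 2.3 and equal correlation 0.5 between occasions.

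**1. Size of the averaged effect.**
- Five post-injection surveys: (0 + 4d)/5 = 0.80d.
- Six scores, including pre-injection: (0 + 0 + 4d)/6 = 0.67d.
- If the immediate score favours control by 0.5d: 3.5d/5 = 0.70d and 3.5d/6 = 0.58d.

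**2. Power of the baseline-adjusted arm test.** For the mean of k surveys adjusted for the pre-injection score, the variance is V = SD² × [(1 + (k − 1)ρ)/k − ρ²]. With arm effects 0, Δ, Δ, the noncentrality is λ = 20 × (2/3) × Δ² / V, on 2 and 56 df.
- Four later surveys, Δ = 1.5: V = 5.29 × (0.625 − 0.25) = 1.984; λ = 30/1.984 = 15.1; power 93%.
- Five surveys, Δ = 0.80 × 1.5 = 1.2: V = 5.29 × (0.60 − 0.25) = 1.852; λ = 19.2/1.852 = 10.4; power 81%.

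Simulations of this case gave 79% to 81% against 93%. With unequal SDs and decaying correlation the loss was smaller: 71% against 77% in one set of assumptions, and 59–60% against 64–65% in another. The range of loss is therefore about 5 to 14 points. Without baseline adjustment (SD 2.5, correlation 0.5) the arm test falls from 67% to 49%.

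**3. Arm-by-time, with an arm difference δ at the immediate survey only.** For six occasions, λ = 20 × (2/3) × δ² × (1 − 1/6) / [SD²(1 − ρ)], on 10 and 285 df.
- δ = 1: 11.11/2.645 = 4.20; rejection 22%.
- δ = 1.5: 25/2.645 = 9.45; rejection 50%.

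Simulated values ran from 15% to 22% for 1 point and from 32% to 51% for 1.5 points. With a Greenhouse-Geisser correction under decaying correlation they were 12% and 30%.

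**4. Arm-by-time, with d = 1.5 at the later surveys only.** The factor (1 − 1/6) is replaced by the sum of squared deviations of the 0/1 time pattern.
- Six scores: 4 × (1 − 4/6) = 1.333; λ = 30 × 1.333/2.645 = 15.1; power 75%.
- Pre-injection plus four later: 4 × (1 − 4/5) = 0.8; λ = 30 × 0.8/2.645 = 9.07; power 52%.
- Four later surveys alone: the effect is constant, λ = 0, and the test rejects at 5%.

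So adding the immediate score does not dilute this term. Restricting this term to the four later surveys would make it blind to a constant drug effect.

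**5. Direction of any lidocaine difference.** The two anti-inflammatory mixtures hold 1 mL of 1% lidocaine in 2 mL; control is 1% throughout. Control therefore has twice the lidocaine per mL, and a lidocaine-driven immediate difference would favour control.

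**The case against.** Four points on the other side deserve weight.

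- **Inclusion is inferred.** The list under Time points is a survey schedule, and no sentence says that all six scores enter the ANOVA. That stands. Inclusion is still the natural reading of a repeated-measures analysis that excludes nothing, and the silence is itself what needs correcting.
- **Numbness does not mimic a drug benefit.** A reader might infer that lidocaine could pass for an anti-inflammatory effect. The documents do not support this: numbness shared by all arms creates no between-arm difference, and the unequal content points towards control.
- **The two harms belong to different tests.** Dilution applies to the averaged arm effect; the misleading significance applies to arm-by-time. They cannot both be charged to one analysis, and arm-by-time gains power for a later effect when the immediate score is included. This stands.
- **The rejection rates need care.** A 1-point immediate difference is an assumption. If the arms truly differ at that survey, rejecting is not a false positive; the problem is how the result would be read. With unequal SDs and decaying correlation, the uncorrected F test rejected about 8–9% of the time with no arm difference at all, so part of the excess there is non-sphericity.

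The ANOVA also serves a secondary outcome. The SAP reports 10 enrolled, two with complete measurements, and no analysis supported.

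**Conclusion.** The concern holds as a gap in specification with a measurable consequence. As written, the plan allows a score that carries anaesthesia rather than the hypothesised effect into the between-arm NRS analysis, and the result depends on an unstated choice of term.

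The attenuation to 0.80 or 0.67 is arithmetic, given a drug effect that is absent immediately and equal at the four later surveys. The power loss of roughly 5 to 14 points and the rejection rate of about 20% rest on assumed SDs, correlations and effect sizes. Their direction is firmer than their size.

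The documents do not show that the immediate score was certain to be analysed as an efficacy occasion. Because the analysis is secondary and the trial ended early, the point matters mainly for how any data are reported and for reuse of the plan.

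**What to change.** State in the statistical plan that:

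1. The between-arm efficacy test for NRS and for BPI is the arm contrast averaged over the 1-week, 2-week, 4-week and 3-month surveys, with the pre-injection score as covariate. It is not an arm-by-time test on those four surveys, which would have about 5% power for a constant effect.
2. The immediate score is summarised separately by arm, as a description of the anaesthetic and needling response, and does not count towards a claim that one substance is better.
3. The responder outcome is judged at one named later survey, identified as the primary time point.

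The cost is wording only. The immediate survey is still collected and reported; the one downside is that an occasion leaves the efficacy model.

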**Double-blind, prospective comparison of medications used in trigger point injections –  
ketorolac, lidocaine, or dexamethasone**

**NCT:** 03028012

**PI:** [name]

**Report Date:** April 5, 2017

**Type of Report:** Statistical Plan/Analysis

This study was terminated early due to the lack of enrollment and of participant follow-through to substantiated end of study measures. There was not enough reported data to provide statistically pertinent or relevant analysis based on the original statistical plan and analysis (listed below). The enrollment for this study consisted of 10 participants, 2 males, 8 females. Out of the total number of participants enrolled only two participants completed all study measurement requirements. The remaining eight participants only completed some of the required protocol surveys. Reviewing this study statistically it was decided that there was not enough statistical data to report statistically significant data.

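### Repeated-measures ANOVA is the only method for the secondary NRS outcome, with no form or missing-data approach stated; if run on complete rows, one missed score drops a participant

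*Protocol*

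**What the plan says.** The statistical plan in the Protocol (Statistical Methods, Data Analysis and Interpretation) has two sentences. One gives a chi-square test for responders. The other is "Repeated-measures ANOVA testing will be used to identify changes in pain scores". The SAP repeats both unchanged under Original Statistical plan.

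The second sentence is the only method that fits the first secondary outcome, listed as "1. NRS improvement". Under Outcomes, the NRS is taken before and after injection. Under Time points, "Participants will fill out a pre-injection survey that contains demographic information and pain- and function-related questions", and then "Participants will also complete a survey at the following time points": immediately, and at 1 week, 2 weeks, 4 weeks and 3 months. That makes six scores per participant if the NRS is asked at every survey. The text implies this but does not list it visit by visit.

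Neither document mentions missing data, imputation, an analysis population, a mixed model or a dropout allowance. The opening part of the Protocol was not available for review, but its statistical section and the SAP were.

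On follow-up, the SAP's opening statement reports that two of ten participants completed all study measurements and that "The remaining eight participants only completed some of the required protocol surveys".

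**The concern.** Classical repeated-measures ANOVA needs a full row for each participant. Someone with five of the six scores contributes nothing, and the five scores already collected are thrown away. Gaps are foreseeable when surveys run to 3 months and participation requires no study-specific visits, and incomplete follow-up did occur.

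Because the form is not stated, the choice between deleting and keeping incomplete participants would be made after the data are seen. At stake are precision and power for a secondary outcome with 20 per arm. The primary responder comparison is not part of this point.

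**Working it through.** **Inputs from the documents.** Planned size 60, 20 per group (Power Analysis); one pre-injection and five post-injection surveys (Time points). The plan gives no sample-size or power figure for the NRS, so there is none to reproduce. The 60 was sized on responder percentages and is taken as given here.

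**Assumptions, because the documents give no figures.** SD 2; correlation 0.5 between any two scores of one person; both anti-inflammatory arms 1.5 points lower than lidocaine from week 1, with no difference before that; two-sided 5% test; data missing completely at random; pre-injection and immediate surveys always completed. Average completion q over the other four surveys is 95, 90 or 80%.

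**Step 1: complete rows out of 60, under three patterns with the same q.**
- Independent misses: 60 × q⁴ = 48.9 / 39.4 / 24.6.
- Monotone dropout with constant retention s per survey, where (s + s² + s³ + s⁴)/4 = q. This gives s = 0.9796 / 0.9583 / 0.9127, and 60 × s⁴ = 55.3 / 50.6 / 41.6.
- Clustered non-response, within-person correlation 0.5 (beta-binomial): 60 × q(q+1)(q+2)(q+3)/24 = 54.0 / 48.4 / 38.3.

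**Step 2: post-injection scores collected but discarded.** Collected: 60 × (1 + 4q) = 288 / 276 / 252. Kept: 5 × complete rows. At 90%, the discarded shares are:
- independent: (276 − 196.8)/276 = 28.7%
- dropout: (276 − 253.0)/276 = 8.3%
- clustered: (276 − 241.8)/276 = 12.4%

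**Step 3: power of the drug-by-time F test.** Within-subject variance is 4 × (1 − 0.5) = 2. With n complete rows per arm, the noncentrality is n × 1.5² × (2/3) × (4/3) / 2 = n. Here 2/3 is the sum of squares of the centred arm pattern (0, −1, −1), and 4/3 that of the centred time pattern (0, 0, 1, 1, 1, 1). With nothing missing, n = 20, the degrees of freedom are 10 and 285, and power is 88%. With gaps, noncentral-F power was averaged over random missing patterns, first on complete rows only and then by the same F test on every observed score. Only the deletion rule differs within a pair.

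| Pattern | Complete rows of 60 at 95 / 90 / 80% | Post-injection scores discarded | Power, complete rows vs all observed |
|---|---|---|---|
| Independent | 49 / 39 / 25 | 15 / 29 / 51% | 78 vs 87, 65 vs 86, 40 vs 83% |
| Monotone dropout | 55 / 51 / 42 | 4 / 8 / 17% | 84 vs 86, 80 vs 84, 68 vs 80% |
| Clustered | 54 / 48 / 38 | 6 / 12 / 24% | 83 vs 87, 77 vs 85, 64 vs 81% |

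Rows and discarded shares are expected values from the formulas above. Averages over simulated patterns differ from them by at most about one row or one percentage point (for example 41 rows and 18% for dropout at 80%, and 13% for clustered at 90%). Power figures carry simulation error of about one point.

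**Reading the table.** The power lost to deletion at 95 / 90 / 80% completion is 9 / 21 / 43 points if misses are independent, 2 / 4 / 12 under dropout and 4 / 8 / 17 if clustered. The pattern matters as much as the completion rate.

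**The case against.** The strongest reply is that the documents never commit to complete-row analysis. They name a family of methods without its form, factors or covariance structure, and some would describe a mixed model in the same words. That stands: what is established is under-specification, and the harm from row deletion is conditional.

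Four stronger readings are tempting but not supported.
- *Modest non-response must discard a large share of the data.* This holds only if missed surveys are independent within a person. Nothing in the documents supports that pattern, and people who stop answering often stay missing. Under plain dropout at 90 to 95% completion the loss is small.
- *Two of ten measures NRS retention.* The SAP counts all study measurements, which include other survey content such as the BPI. It shows that follow-up was incomplete but gives no rate for complete NRS rows, so no interval for NRS retention should be drawn from it.
- *The ANOVA was not meant to compare drugs.* The sentence names no drug factor, but the Protocol also says "The research component of this study is to compare the efficacy of three substances". The omission is a wording gap, not a separate error.
- *The proposed model would have the power in the all-observed column.* Those figures isolate row deletion in one F test with a simple covariance. An unstructured model on five occasions estimates 15 covariance parameters, and its power was not computed.

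It is also fair to say that the outcome is secondary, and that the trial stopped at 10 participants without carrying out the planned analysis.

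**Conclusion.** The point holds in a conditional form and is minor. The plan for the NRS names one method, states neither its form nor a missing-data approach, and covers six planned scores. If the usual complete-row form were applied, any single gap would remove a participant. At an assumed 90% average completion that discards between about 8% (dropout) and 29% (independent misses) of the post-injection scores, and costs about 4 to 21 power points at a 1.5-point effect. At 95% completion under dropout the cost is about 2 points; at 80% with independent misses it is about 43.

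These sizes rest on the assumed SD, correlation, effect, completion rates and missing-completely-at-random patterns. They also rest on two inferences: that the NRS is asked at every survey, and that the complete-row form is used. No reported result is affected.

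**What to change.** Replace the ANOVA sentence in the Protocol and SAP with, for example:

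*NRS at the five post-injection time points will be analysed with a likelihood-based mixed model for repeated measures using all available observations, with drug, time, drug-by-time and baseline NRS as fixed effects and a small-sample degrees-of-freedom correction (a simpler covariance structure if unstructured does not converge). Each anti-inflammatory drug will be compared with lidocaine, with 95% confidence intervals, as supportive secondary comparisons.*

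The cost is a change of wording and standard software, with no new data or visits. The downsides are reliance on a missing-at-random assumption and more covariance parameters to estimate. The change would not have rescued the 10-participant trial and applies only if the study is restarted or the plan reused.

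### The planned NRS analysis names no baseline covariate; adjusting for the pre-injection score would usually sharpen the arm comparison, by an amount the documents do not let one fix

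*Protocol*

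**What the plan says.** The protocol lists "NRS improvement" as a secondary outcome, with improvement on the Brief Pain Inventory (BPI) beside it. Its Outcomes list has the NRS (0–10) taken before and after injection. The Time points section adds: "Participants will fill out a pre-injection survey that contains demographic information and pain- and function-related questions". Five post-injection surveys follow: immediately, and at 1 week, 2 weeks, 4 weeks and 3 months.

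The whole NRS analysis, in the protocol's Statistical plan and word for word in the SAP's Original Statistical plan, is: "Repeated-measures ANOVA testing will be used to identify changes in pain scores". The factors, the role of the pre-injection score, the covariance structure and the contrast between arms are not given. No analysis is named for the BPI.

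The primary outcome is responder status (more than 50% NRS relief), for which "Chi-square analysis will be used to identify differences in responders between groups". The sample size rests on responders: "We have identified a sample size of 60 subjects (20 per group) as being sufficient". No SD, correlation or power is stated for the NRS.

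**The concern.** The aim is to compare three injected substances, so the useful NRS result is a difference between arms. The words changes and improvement both need a pre-injection reference, and the one named method carries no covariate. The plan therefore reads most naturally as a comparison of change scores, or of the group-by-time interaction that plays the same part.

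A change score subtracts the whole baseline, which is the best correction only when the regression slope of follow-up on baseline equals 1. At any other slope it leaves avoidable noise in the comparison. When the slope is below 1 it also over-corrects an arm that starts high or low by chance. If the group main effect were read instead, with the pre-injection score as one of six levels, it would average in a score taken before any treatment.

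With 20 per arm, chance baseline differences are not trivial. Adjusting for a score already collected needs no further participants.

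**Working it through.** **The plan's own figure.** There is none for the NRS. The only planning figure, 60 in total, is for responders (5% versus 15%) and does not enter this check. It is not reproduced from those rates either (141 per arm at two-sided 5% and 80% power), but that is a separate matter.

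**Inputs from the documents.** 20 per arm, three arms, one pre-injection and five post-injection scores.

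**Assumed inputs.** ρ (baseline to follow-up correlation) from 0.2 to 0.8; SD_b before injection and SD_f after it. The documents give none of these.

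**Formulas at one time point, per participant.**
- Change score: V_ch = SD_b² + SD_f² − 2ρ·SD_b·SD_f
- Baseline-adjusted: V_adj = SD_f²(1 − ρ²)
- Difference: V_ch − V_adj = (SD_b − ρ·SD_f)², which is never negative

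**Equal SDs.** V_ch = 2(1−ρ)SD² and V_adj = (1−ρ²)SD², so the ratio is (1+ρ)/2 and the variance reduction is (1−ρ)/2.

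| ρ | variance reduction | SE reduction, 1 − √((1+ρ)/2) | 20 per arm performs like, 20/((1+ρ)/2) |
|---|---|---|---|
| 0.2 | 40% | 22% | 33 |
| 0.3 | 35% | 19% | 31 |
| 0.4 | 30% | 16% | 29 |
| 0.5 | 25% | 13% | 27 |
| 0.6 | 20% | 11% | 25 |
| 0.7 | 15% | 8% | 24 |
| 0.8 | 10% | 5% | 22 |

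**Unequal SDs (assumed SD_b = 1.7, SD_f = 2.5).** V_ch = 2.89 + 6.25 − 8.5ρ and V_adj = 6.25(1−ρ²).

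| ρ | V_ch | V_adj | variance reduction |
|---|---|---|---|
| 0.3 | 6.59 | 5.69 | 13.7% |
| 0.4 | 5.74 | 5.25 | 8.5% |
| 0.5 | 4.89 | 4.69 | 4.1% |
| 0.6 | 4.04 | 4.00 | 1.0% |

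The gain nearly vanishes at ρ = 0.6 because the regression slope is then 0.6 × 2.5/1.7 = 0.88, close to the slope of 1 that a change score imposes.

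**Power for an assumed 2-point difference** (two arms of 20, two-sided 5%, follow-up SD 2.5). With equal SDs, change score versus adjusted: 55% versus 73% at ρ = 0.3, and 69% versus 81% at ρ = 0.5. With SDs 1.7 and 2.5: 67% versus 73%, and 80% versus 81%.

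**Mean of the five post-injection scores** (same correlation ρ between all pairs of scores, equal SDs, variances in units of SD²). Let P = (1+4ρ)/5. Then V_ch = P + 1 − 2ρ and V_adj = P − ρ². At ρ = 0.3 these are 0.84 and 0.35, a 58% reduction; at ρ = 0.6 they are 0.48 and 0.32, a 33% reduction. With SDs 1.7 and 2.5 the reductions are 29%, 8.5% and 2% at ρ = 0.3, 0.5 and 0.6.

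**Cost of estimating a slope.** Variance is inflated by 1 + 1/(60 − 5) = 1.018, about 2%. With equal SDs the net reduction is 33.8% at ρ = 0.3 and 18.5% at ρ = 0.6. With SDs 1.7 and 2.5 it is −0.8% at ρ = 0.6.

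**Chance imbalance.** The SE of the baseline difference between two arms of 20 is 1.7 × √(2/20) = 0.54 points.

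**The case against.** The strongest reply is that the documents never say how the baseline enters the model. A reader might infer that the plan fixes the pre-injection score as a repeated level or subtracts it. The sentence supports that as the natural reading but does not state it. What can be said firmly is that no baseline covariate is named. Nor is keeping the baseline among the repeated outcomes inefficient in itself: a longitudinal model that holds the baseline mean equal across arms has essentially the same precision as covariate adjustment. This stands, and the fix allows for it.

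A reader might also infer a definite loss of 20–35% of precision. The documents do not support that. The range is a share of variance, not of the standard error, and it needs ρ between 0.6 and 0.3, equal SDs and one follow-up. With other plausible SDs it falls to a few per cent. Nor would every interval become narrower at no cost: where the slope is already near 1, the price of estimating it can slightly exceed the gain.

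Thirdly, the NRS analysis is secondary, the responder outcome already uses the baseline through its definition, and the SAP reports termination with 10 enrolled and two completing all measures. All true. The change cannot rescue these data, but early termination does not make the plan's sentence adequate, and the point applies to the plan as written and to any reuse of it.

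**Conclusion.** The point holds as a missed improvement in a secondary analysis. The plan collects the pre-injection NRS, compares arms on improvement, and names no baseline adjustment. Under the natural change-score reading, and apart from about 2% for the estimated slope at N = 60, adjustment is never less precise and is usually more so.

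Its size is conditional. Per time point with equal SDs the variance reduction is 40% to 10% for ρ 0.2 to 0.8; with SDs of 1.7 and 2.5 it is 14% to 1% for ρ 0.3 to 0.6. For an average over the five surveys it can be larger. All SDs and correlations here are assumptions.

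A reader might take this as a flaw of validity. It is not: under randomisation a change-score comparison is unbiased, and what is at issue is efficiency and the handling of chance imbalance.

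**What to change.** In the protocol's Statistical plan and the SAP's Original Statistical plan, replace the repeated-measures sentence with wording such as:

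> Post-injection NRS will be compared between arms in a repeated-measures model with arm, time, arm-by-time, pre-injection NRS and pre-injection NRS-by-time. Pre-injection NRS is the score recorded before the first injection and is not a repeated outcome. An equivalent longitudinal model that constrains the baseline mean to be equal across arms may be used instead. Results are baseline-adjusted differences, each anti-inflammatory arm minus lidocaine, with 95% confidence intervals. BPI will be analysed in the same way with pre-injection BPI.

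The baseline-by-time term is there because the correlation with baseline may weaken between the immediate and 3-month surveys. Tying the baseline to the first injection is needed because the protocol allows up to four injections.

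Cost: a short change of wording and a few degrees of freedom, about 2% of variance per covariate term at N = 60. No new data, visits or participants are required.
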